- 2) Small diameter retraction cord, after it has been hydrated with Hemodent for 10 minutes, is tucked around the tooth in the space between it and its surrounding gum tissue. A second larger diameter retraction cord, also hydrated with Hemodent, will be placed over the first cord and tucked around the tooth. These cords will be left in place for a minimum of 8 minutes. These cords temporarily push the gum tissue back away from the tooth. (Before making the impression, the 2nd larger cord is removed, and the gums will stay back long enough for the impression material to seep around the tooth, thus allowing it to capture a copy of the entire tooth preparation.)
- 3) After a minimum of 8 minutes, the larger 2nd cord will be removed, and the tooth dried. Quickly, after confirmation of a dry field, the light body consistence impression material is syringed around the prepared tooth and across the occlusal surfaces of adjacent teeth.
- 4) An impression tray that has been filled with the heavy body consistency impression material is then placed over the arch of teeth, and gently pressed into place to ensure the teeth are completely covered with a uniform thickness of impression material. As the different impression material consistencies set, they fuse together into a single unit.
- 5) When removed from the mouth, the impression should contain a negative copy of both the prepared tooth and the teeth of that jaw.

Cordless Impression Procedure:

- 1) The prepared tooth is washed and dried, and assure hemostasis.
- 2) Apply B4 + surface optimizer.
- 3a) If 1 prepared tooth requiring an indirect restoration is being impressed, a single size (0.7mL) unit dose cartridge will be inserted into the digit power dispenser. If more than 1 prepared tooth requiring an indirect restoration is being impressed, a multi size (1.6mL) unit dose cartridge will be inserted into the digit power dispenser.
- 3b) Using the digit power dispenser, unit dose cartridge, and intrasulcular mixing tip, depress foot pedal and gently insert tip into the gingival sulcus of the prepared tooth, slightly apical to the preparation finish line. Material should flood the sulcus. Make sure to dispense material ahead of the intrasulcular tip, and completely around the prepared finish line, and then the tooth.

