- 4) An impression tray that has been filled with the heavy body consistency impression material is then placed over the arch of teeth, and gently pressed into place to ensure the teeth are completely covered with a uniform thickness of impression material. As the different impression material consistencies set, they fuse together into a single unit.
- 5) When removed from the mouth, the impression should contain a negative copy of both the prepared tooth and the teeth of that jaw.

The clinician will record the impression technique, type of impression material used; whether tray adhesive was used; the tray material; the type of tray used; the number of units requested; the time required to obtain the first impression (start and end of impression taking is defined above for each procedure), and the total number of impressions produced until an adequate impression was made. Also recorded will be the clinic and resident year if placed in a graduate clinic and the subject's age and sex. Unique id numbers not related to clinical record will be used.

The impressions will be photographed, digitally scanned, saved in black and white, and then collectively evaluated at a later time based on a criteria evaluation form by two calibrated evaluators. The evaluators (also referred to as expert examiner) will assess each impression for errors in the finish line; in the tray/material; and errors with gingival displacement/hemostasis as primary outcomes. The number of errors can range from 0 to 13.

Patient discomfort will be assessed using the FACES visual picture pain scale rated from 1-10 based on the following question posed at 4 points during treatment; "How much discomfort are you experiencing at this point in treatment?" This question will be asked at the beginning of the treatment appointment, immediately before the impression procedure is initiated, immediately after the impression procedure is completed, and again at the completion of the treatment appointment. Each question will be rated on a scale of 1 to 10. The total score indicated by the sum of the 4 questions will be analyzed.

Patient consent will be obtained prior to treatment and the impression. This may occur at a prior treatment planning visit or at the treatment visit.

Inclusion Criteria:

- Patients must be adult males or females 18 years of age or older.
- Patients must be able and willing to follow study procedures and instructions.

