Descriptive statistics for all study variables will be computed by impression group and used to summarize the procedural materials used in the impression and the outcomes. The primary outcomes are the number errors of the impression in the finish line; in the tray/material; and errors with gingival displacement/hemostasis (number of errors can range from 0 to 13), the time to complete the impression, and patient discomfort (range from 0 to 40). Since the outcomes are unlikely to be normally distributed, the Wilcoxon rank sum test will be used as the primary statistical test to assess whether the quality of impressions, time, or patient discomfort made with a cordless gingival displacement procedure is different than with a corded technique. To adjust for additional covariates [clinic providing care, jaw, procedural materials], Poisson regression will be used to assess the relationship between the primary outcomes and the covariates of interest, including impression group with a primary interest in estimation using confidence intervals.

The lack of historical data comparing the proposed outcomes between the two impression groups makes a sample size calculation difficult. For this exploratory study which is time constrained as a thesis project, a sample size calculation was done using an effect size which may be larger than the clinically meaningful effect size. A sample size of 30 in each group will have 80% power to detect a probability of 0.709 that an observation (number of total errors) in the Cordless group is less than an observation in the Corded group using a Wilcoxon (Mann-Whitney) rank-sum test with a 0.05 two-sided significance level.

Budget

Materials	Amount needed	Estimated costs
Aquasil Ultra Cordless Pneumatic Power Dispenser Units (3)	3 systems	Included in normal clinic treatment
Aquasil Ultra Cordless PVS material	Enough for 30 impressions + 10 for practice calibration.	Included in normal clinic treatment
Aquasil Ultra Cordless B4 Pre-Impression Surface Optimizer	Enough for 30 impressions + 10 for practice calibration.	Included in normal clinic treatment
Aquasil Ultra Cordless Ultrathin intra sulcular tips	Enough for 30 impressions + 10 for practice calibration.	Included in normal clinic treatment
Aquasil Ultra PVS materials (heavy and light body)	Enough for 60 impressions + 10 for practice calibration.	Included in normal clinic treatment

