GingiBraid retraction cord	12 containers- sizes: 00,0,1,2; (3) of each.	Included in normal clinic treatment
Hemodent	3 bottles + 1 for practice calibration	Included in normal clinic treatment
Viscostat	60 disposable vial/syringe	Included in normal clinic treatment
Impression trays	60 trays + 20 for practice calibration	Included in normal clinic treatment
Impression tray adhesive	3 bottles + 1 for practice calibration	Included in normal clinic treatment
Estimate Total:		

Timeline

The study is planned to last approximately 1.5 years to allow for recruitment and data collection and analysis. The study would ask the participants to come to 2 appointments; it might be possible to consent the patient and perform treatment on the same day, if the patient was scheduled for treatment that day already.

TO BE COMPLETED BY TREATING CLINICIAN:

Patient did not meet inclusion/exclusion criteria and is dropped from the study

Medical/smoking

Probing pocket depths around treatment tooth/teeth of greater than 4mm.

Bleeding on probing around treatment tooth/teeth.

The prepared finish line is greater than 1mm sub-gingival

Patient meets inclusion/exclusion criteria

Patient ID: _____

Impression Group: _____ *Corded* _____ *Cordless*

Clinic: _____ *Dental Faculty Practice*

_____ *Graduate Operative Clinic* _____ *1st* _____ *2nd* _____ *3rd*

_____ *Graduate Prosthodontic Clinic* _____ *1st* _____ *2nd* _____ *3rd*

Patient Age: _____

Gender: _____ *Male* _____ *Female*

Type of impression material used:

Tray adhesive used:

Aquasil Ultra Cordless

Aquasil Ultra

Yes *No*

Tray material:

Metal stock *Plastic stock* *Custom* *Plastic dual arch* *Metal dual arch*

Type of tray used:

Ant quad *Post quad* *Full arch*

Number of units requested:

2-3 FDP *Onlay* *Single crown x _____*

Anterior *Canine* *Premolar* *Molar*

Jaw: *Maxillary* *Mandibular*

Time Required for 1st Impression: _____ minutes and seconds

Number of Impressions Required to Obtain Adequate Impression: _____

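### The adjusted Poisson regression names no variance method for any primary outcome and no analysis unit for time, so the plan does not fix the confidence intervals that the model is meant to give

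*Combined protocol and SAP*

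**What the plan says.** The Statistical Analysis section of the combined protocol and SAP lists three primary outcomes: impression errors ("number of errors can range from 0 to 13"), time to complete the impression, and patient discomfort. The Wilcoxon rank-sum test is the primary test for each.

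One sentence covers the adjusted analysis. It opens "To adjust for additional covariates [clinic providing care, jaw, procedural materials", continues "Poisson regression will be used to assess the relationship between the primary outcomes and the covariates of interest, including impression group", and gives the aim as "with a primary interest in estimation using confidence intervals". The documents mention no dispersion check, scaled or robust standard error, alternative count model or confidence level.

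Three other places bear on this:
- Methods builds discomfort from four ratings of 1 to 10: "The total score indicated by the sum of the 4 questions will be analyzed". The possible range is therefore 4 to 40, although Statistical Analysis gives 0 to 40.
- The treating clinician's form has the entry "Time Required for 1st Impression", to be filled in as minutes and seconds. That is a recording format. No section says what number enters the model.
- Methods lists the recorded materials: "type of impression material used; whether tray adhesive was used; the tray material; the type of tray used".

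**The concern.** Poisson regression fixes how the mean depends on the covariates. Its default standard errors also take the variance to equal the mean. That can be a fair first approximation for a count of errors, but time is continuous and discomfort is a bounded rating sum, so for these two the design gives no reason to expect it. Where the true variance is larger than the mean, default intervals are too narrow; where it is smaller, they are too wide.

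Time has a further problem. The variance-equals-mean assumption depends on the unit, so two analysts who follow the same sentence with default output can report the same ratio with very different precision.

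The interval is the stated product of this model. The regression is also the only planned analysis containing clinic and jaw, so the secondary aims on jaw and clinician experience depend on it for estimates.

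**Working it through.** **Inputs.** From the documents: 100 participants in balanced blocks (about 50 per arm), 30 per group in the sample-size statement, two-sided 0.05. The confidence level is not stated; I take 95% (z = 1.96). The documents give no means or SDs, so all of those below are assumptions.

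**1. The plan's own figure.** Noether's formula: N = (1.960 + 0.842)² / [12 × 0.25 × (0.709 − 0.5)²] = 7.849 / 0.1310 = 59.9, so 30 per group, with power 80.1%. The stated figure reproduces. It concerns the Wilcoxon test and is not in question.

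**2. Unit of time.** The default Poisson SE of a log ratio between two arms is sqrt(1/S1 + 1/S0), where S1 and S0 are the arm totals. Going from minutes to seconds multiplies both totals by 60. The ratio is unchanged and the SE is divided by sqrt(60) = 7.75. Covariates do not alter this, because the model-based information is proportional to the fitted means. No assumption about spread is needed.

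**3. What the interval looks like** (50 per arm, corded vs cordless). For 12 vs 5 min (SD 3, 1.5):
- default, minutes: sqrt(1/600 + 1/250) = 0.0753
- default, seconds: 0.0753 / 7.75 = 0.0097
- correct: sqrt([(3/12)² + (1.5/5)²] / 50) = 0.0552

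| Assumed times | Ratio | Minutes, default | Seconds, default | Correct variance |
|---|---|---|---|---|
| 12 vs 5 min (SD 3, 1.5) | 0.417 | 0.360-0.483 | 0.409-0.425 | 0.374-0.464 |
| 15 vs 10 min (SD 5, 4) | 0.667 | 0.595-0.747 | 0.657-0.676 | 0.577-0.770 |

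In minutes, the first interval is too wide and the second too narrow.

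**4. Coverage for time.** With r = default SE / true SE = sqrt(mean/variance), coverage of a nominal 95% interval is 2Φ(1.96r) − 1.
- Mean 15, SD 5: r = sqrt(15/25) = 0.775, coverage 87% in minutes; r = 0.10 in seconds, about 15%.
- Mean 5, SD 1.5: r = sqrt(5/2.25) = 1.49, coverage 99.7% in minutes; r = 0.19 in seconds, 29%.

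Simulation (gamma times, 5,000 replicates per scenario, 50 per arm, adjusted for clinic and jaw) agrees:
- equal means of 5-15 min, SD 1.5-5: 87-99.8% in minutes, 15-30% in seconds
- unequal means, corded 12-15 min vs cordless 5-11 min: 87-99.4% in minutes, 16-27% in seconds

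These ranges belong to the assumed spreads. At mean 15 and SD 7.5, r = sqrt(15/56.25) = 0.52 and coverage in minutes is 69%.

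**5. Error count and discomfort.** The same formula, by variance/mean ratio: 95% at 1, 89% at 1.5, 83% at 2, 74% at 3.
- Errors: 13 independent items at probability 0.2 have mean 2.6 and variance 2.08, giving 97%. An inter-item correlation of 0.2 raises the variance to 2.08 × (1 + 12 × 0.2) = 7.07, giving 76-77%.
- Discomfort: mean 8, SD 2 gives 99%; mean 12, SD 6 gives 74%.

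Both directions are possible, and the documents do not show which applies.

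**6. Which remedy works.**
- Five parameters (intercept, arm, two clinic terms, jaw), 50 per arm: an uncorrected sandwich (HC0) covers 92.9-94.6% and Pearson scaling 93.8-96.1%.
- Twelve parameters: adhesive adds 1, tray material 4 and tray type 2 (level frequencies assumed). HC0 covers about 92-94% at 50 per arm and 89-93% at 30 per arm; Pearson scaling about 93-96%.
- A sandwich with the simple degrees-of-freedom correction (HC1) was run only with five parameters (1,000 replicates): 92.6-95.1% at 50 per arm and 92.7-94.3% at 30.

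Pearson scaling assumes one common variance/mean ratio. In the 12 vs 5 min example the arms have 9/12 = 0.75 and 2.25/5 = 0.45, average 0.60. The scaled SE is sqrt(0.60) × 0.0753 = 0.0583 against a correct 0.0552, a small loss.

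**The case against.** The strongest reply is that this is under-specification and not a wrong analysis. Poisson regression names a model for the mean; with scaled or robust errors it is sound for all three outcomes, and an analyst might use them unprompted. Times noted in minutes and seconds would most naturally become decimal minutes, where default intervals in the assumed scenarios are sometimes conservative. The seconds figures need two choices that the plan does not make: total seconds and unscaled errors. For a bounded error count, Poisson regression is conventional. The Wilcoxon tests are primary, and the study is an exploratory, time-limited thesis project.

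Most of this stands, and it limits the weight of the point. It does not close the gap: the plan states intervals as the purpose and leaves open the choices that determine them.

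A reader might go further and infer that the time intervals will cover only 15-30%, or that the trial's conclusion on time is unsafe. The documents do not support that. They prescribe neither seconds nor default errors, and in both examples of step 3 either unit excludes a ratio of 1. The conclusion moves only for a small difference: at 12 vs 11 min (SD 4), 1 is excluded in 33% of trials in minutes, 92% in seconds and 25% with robust errors. So small a difference is less plausible if the cord wait is timed ("These cords will be left in place for a minimum of 8 minutes"), but whether it counts is not clear from the procedure steps.

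**Conclusion.** The point holds as a gap in the adjusted analysis that should be fixed. The 7.75-fold difference in the standard error for time between minutes and seconds is exact. Everything else about size rests on assumed means and SDs: at 50 per arm, about 87-99% coverage for time in minutes, about 15-30% as a worst case in seconds with default errors, and about 83% for the error count if its variance is twice its mean. For the error count and discomfort, neither the direction nor the size of the error can be known from the documents.

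The effect is confined to the precision reported for the adjusted estimates. The primary Wilcoxon tests and the sample size stand.

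**What to change.** Add one sentence to Statistical Analysis: for all three outcomes, confidence intervals (95%) will use Pearson-scaled (quasi-Poisson) standard errors, or sandwich standard errors with a small-sample correction, one of which is named in advance; time will be analysed in decimal minutes. Pearson scaling is the better-supported choice, because it kept about 93-96% coverage in the twelve-parameter model, where the corrected sandwich was not tested. An uncorrected sandwich should not be used. With either permitted option the interval for the time ratio no longer depends on the unit. Stating the unit makes the remaining output reproducible.

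The cost is wording only: no new data and no change to the sample size or procedures. Some intervals will widen (by sqrt(2) = 1.41 on the log scale if the variance is twice the mean), and the choice must be fixed before analysis.

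A separate point concerns the same sentence of the plan. Itemise the procedural materials and leave out impression-material type. Its two options on the clinician's form, Aquasil Ultra Cordless and Aquasil Ultra, closely track the randomised arms. If material and arm coincide, the arm effect cannot be estimated. With k discordant records in each arm of 50, the arm-material correlation is 1 − 2k/50, and the variance of the arm effect rises by about 1/(1 − correlation²): roughly 13-fold for k = 1, 6.5-fold for k = 2 and 2.8-fold for k = 5. Tray adhesive, tray material and tray type can stay.

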Appendix B:

TO BE COMPLETED BY EVALUATORS

Evaluator: **ONE** **TWO**

Patient ID: _____

Errors in the finish line:

Voids/Bubbles Lack of wash material Tearing

Errors in the tray/material:

Cotton roll attached Inadequate fusion of viscosity Lack of polymerization

Show through of occlusal/incisal edges

Inadequate retention Pressure of tray on soft tissue Void on the preparation

Errors with gingival displacement/hemostasis:

Tissue over finish line Retraction cord attached Blood on impression
